6.4. ACCOUNTABILITY

All supplies will be maintained under adequate security by the responsible member of the Pharmacy staff.

The Investigator will ensure that study treatment is only administered by designated staff within the center. In particular, for U.S. sites, the Investigator will ensure that study treatment is only administered by those named as sub-investigators on the FDA form 1572 and designated staff.

When Investigational Product is received by the Pharmacist (or designee), he/she will check for accurate delivery and acknowledge receipt by signing and dating the documentation provided by or on behalf of PPD and returning it to PPD. A copy will be retained for the Investigator/Pharmacy file.

The dispensing of the Investigational Product will be carefully recorded on appropriate drug accountability forms (these will be provided by PPD) and an accurate accounting will be available for verification by the CRA at each monitoring visit.

Drug accountability records will include:

- confirmation of delivery of the Investigational Product to the trial site,
- the inventory at the site (ampoules/bags),
- the use by each patient,
- the return to Dompé or alternative disposition of unused product(s),
- accounts of any Investigational Product accidentally or deliberately destroyed,
- accounts of any reserve ampoules used.

They should include dates, quantities, batch numbers, expiration dates (if applicable), and any unique code numbers assigned to the Investigational Product(s) and/or patients. Investigators should maintain records which document adequately that:

- the patients were provided the doses specified by the protocol/amendment(s),
- all Investigational Product provided was fully reconciled.

The PPD will review the drug accountability forms and check all Investigational Product ampoules (both unused and used) prior to making arrangements for their return to Dompé, or authorizing their destruction by the study site.

Investigational Product which has been dispensed to a patient and returned unused will not be re-dispensed to a different patient.

Unused Investigational Product must not be discarded or used for any purpose other than the present study. Any remaining test material at the end of the trial will be returned to Dompé or disposed of, as determined by the Sponsor.

6.4.1. Assessment of compliance

Compliance will be assured by the person(s) within the center in charge of Investigational Product administration.

Immediately before the start of each 24-hours treatment period, the removable label on the Infusion Bag will be detached and attached to the relevant page of the CRF. Actual date and time of infusion start, switch of infusion rate (first 24 hours period only) and end of infusion will be recorded in the CRF, as well as infusion rates in each period.

Compliance with the study product dosing schedule will be verified by a CRA during on-site monitoring visits, as per records in the CRF, versus accountability records.

6.5. CONCOMITANT THERAPY

Any medications required for the patient's welfare are permitted and will be given at the discretion of the Investigator, except for drugs described in paragraphs below.

Administration of all prior and concomitant medications, apart from the agents listed below, from the time of enrolment until 10 days after the end of study drug administration or until hospital discharge (whichever occurs earlier) will be reported in the appropriate section of the CRF. For the intervals between 10 days or hospital discharge up to 12 month visit, only medications used for immunosuppression, prophylaxis of infections, and AE that the Investigator assesses as at least possibly related to the Investigational Product will be reported.

All the details as per the CRF fields (sequential number, drug name, indication, starting dose, doses at month 1, 6, and 12, route of administration, start/stop dates) will be recorded for the medications used for immunosuppression and prophylaxis of infections. Only the sequential number, the drug name, the indication and the start date will be recorded for all the other concomitant medications.

The following agents do not need to be recorded:

- Saline and other hydration solutions (including additional electrolytes)
- TPN and enteral feeds
- Homeopathic medications
- Elective vitamins and minerals
- Topical agents (apart from inhaled) with no or negligible systemic absorption
- Osmotic laxatives and locally acting antacids

6.5.1. Immunosuppressive therapy

Neither guidelines nor formal consensus on "best" or "standard" immunosuppressive strategies after human lung transplantation are currently available. Therefore,

immunosuppression after lung transplantation is derived from the wider experience gained in renal and heart transplant recipients integrated by the results of specific lung trials.

6.5.1.1. Induction

Data from the International Society for Heart and Lung Transplantation (ISHLT) registry indicate that about 45% of lung transplant recipients receive some type of induction therapy, mainly polyclonal antilymphocyte preparations or anti-interleukin (IL)-2-receptor antibodies. The use of Orthoclone OKT3 has been frequently associated to a cytokine release syndrome, which may induce cardiopulmonary instability. Also, experience with anti-CD52 (Campath) in the specific clinical setting is very limited. Therefore, **induction with Orthoclone OKT3 or Campath will not be allowed in the trial.**

Induction therapy will not be mandatory in this trial and the decision, including the choice of the immunosuppressive agent, with the exclusion of Orthoclone OKT3 and Campath, will be based on center's practice.

6.5.1.2. Maintenance

At the present time, maintenance with a triple-drug regimen can be considered the norm. Therefore, this study will follow the common practice currently in use, recommending a triple-drug regimen of either cyclosporin A or tacrolimus, plus steroids (at a moderate dose in the first seven days), plus either azathioprine or mycophenolate mofetil/mycophenolic acid.

The use of sirolimus will be discouraged, at least in the first three months after lung transplantation, as cases of bronchial anastomotic dehiscence, most fatal, have been reported in de novo lung transplant patients when the drug has been used as part of an immunosuppressive regimen. Programs intending to use sirolimus in the first three months should refrain from enrolling such patients in the trial.

Monitoring strategies for dose adjustment as well as strategies for weaning steroids will be as per center's practice.

6.5.1.3. Treatment of acute and chronic rejection

Treatment of acute rejections will be handled as per center practice.

Treatment of established chronic rejection is currently not supported by evidence obtained in adequately designed clinical studies. Any strategy deemed useful by the Investigator will be allowed.

6.5.2. Prophylaxis of opportunistic infections

Prophylaxis of opportunistic infections will be handled as per center practice.

6.5.3. Other treatments

Nitric Oxide, Surfactant, Prostaglandin E1 will be administered as per center practice.

7. STUDY PROCEDURE AND ASSESSMENTS

A schedule for the tests and evaluations to be conducted in this study is found in the flow chart in Appendix 4. A list of acceptable assessment/procedure time windows is detailed in Appendix 6.

7.1. SCREENING AND RANDOMIZATION

Potential study patients will be identified whilst on the center transplant waiting list. On arrival at the center for transplantation, consented patients will undergo confirmatory screening for the study.

Compliance with inclusion/exclusion criteria will be verified vs demographic and clinical information available as per Organ Procurement Agency - e.g. United Network for Organ Sharing (UNOS) - form and standard clinical practice.

Laboratory tests (hematocrit, hemoglobin, red blood cells, platelets, white blood cells, differential white blood cells count, sodium, chloride, potassium, bicarbonate, serum creatinine, blood urea nitrogen, total bilirubin, ALT, AST, prothrombin time or international normalized ratio, partial thromboplastin time) will be performed by local laboratories.

Screening also includes measurement of BP, HR, body weight (kg), and testing for renal and hepatic function, as well as for extra-respiratory tract site of infection.

Renal function will be evaluated by CL_{Cr}, calculated according to the following formula (*Cockcroft-Gault; 1976*):

$$\text{Male: CL}_{Cr} = \frac{[140 - \text{age (years)}] \bullet \text{Weight (kg)}}{\text{Serum Creatinine (mmol / L)} \bullet 815}$$

$$\text{Female: CL}_{Cr} = \frac{[140 - \text{age (years)}] \bullet \text{Weight (kg)}}{\text{Serum Creatinine (mmol / L)} \bullet 815} \bullet 0.85$$

Hepatic function will be evaluated by bilirubin (mg/dL) and transaminases (ALT and AST).

Extra-respiratory tract sites of infection will be diagnosed by blood culture(s) and/or fever associated with other signs of systemic sepsis syndrome. Previous results of blood cultures can be used to verify inclusion criteria, provided that the sample has not been obtained earlier than 72 hours prior to randomization.

Eligible patients will be randomized (randomization number assigned) by an Investigator or designee before proceeding to the operating room. The Investigator will forward to the Pharmacy an order to start preparation of Investigational Product dosing solution.

A screening form will be completed for all patients who signed the Patient Informed Consent Document, regardless of sequent entry into the study. Patients will be identified by their

initials and date of birth; in addition their race, sex and reasons for exclusion from the study will be recorded.

If entered into the study, the following recipient data will be recorded in the CRF:

- demographic, i.e. age, sex, race, weight, height,
- immediate pretransplant and transplant clinical information as per Organ Procurement Agency - e.g. UNOS - form,
- results of laboratory tests.

7.2. ORGAN PROCUREMENT

Standard protocols for procuring and preserving donor lungs will be used. Lungs will be resected en bloc following systemic heparinization.

Lungs will be washed by anterograde plus retrograde perfusion via the pulmonary artery with Low Potassium Dextran (Perfadex®) - based solution (with or without additions as per center practice) at 4°C. The lungs will be transported in the partially inflated state immersed in Perfadex® solution at 4°C.

Donor lung data will be recorded in the CRF as per Organ Procurement Agency - e.g. UNOS - form.

7.3. OPERATIVE COURSE

In principle, standard surgery procedures, excluding possible graft reflush with leukocyte depleted blood, will be applied as per center practice. However, it is suggested to adopt whenever possible, the following strategies:

- Application of topical hypothermia during implantation.
- After implantation, blood flow will be progressively, in a controlled way, restored over a period of up to 10 minutes (minimum 2 min).
- Protective ventilation strategy will be adopted during the initial period of reperfusion. It is suggested that the newly implanted lung allograft is gently reinflated with a sustained airway pressure of 20 cmH₂O before reperfusion and then ventilated with FiO₂ of 50%, PEEP =5 cmH₂O, and pressure control ventilation limiting peak airway pressures to 20 to 25 cmH₂O. After reperfusion has occurred, changes of ventilation will be directed by the anesthesiologist according to his/her judgment of the functional status of the implanted lung.

Relevant operative details will be recorded in the CRF, including gross abnormalities of the donor lung(s), duration of cold and warm ischemia, time of reperfusion, use and duration of cardiopulmonary bypass, lung reduction procedures, anastomotic difficulties, hypoxemia, and pulmonary edema, use of nitroglycerin/nitric oxide/inhaled prostacyclin/surfactant.

7.4. ADMINISTRATION OF INVESTIGATIONAL PRODUCT IN THE OPERATING ROOM

The infusion Bag No. 1, containing the dosing solution matching the patient randomization number, should be available in the operating room prior to anesthesia induction.

Infusion of the Investigational Product will start approximately 2 hours before the anticipated time of reperfusion of first allograft. The surgeon will identify the time to start study drug infusion.

The infusion pump will be set to provide the infusion rate corresponding to the loading dose. The loading dose will be infused for 30 min. Thereafter, the infusion rate will be reduced to provide the maintenance dose. Infusion rate (mL/hour) corresponding to each unit increment (kg) of body weight, is reported in Appendix 3.

Immediately before the start of infusion, the removable label on the Infusion Bag will be detached and attached to the relevant page of the CRF. Starting time of drug administration, time of switch to maintenance dose and infusion rates will be recorded in the CRF.

7.5. ADMISSION TO ICU

7.5.1. Arrival to the ICU

Date and time of ICU admission will be recorded in the CRF.

All patients will be mechanically ventilated through a oral endotracheal tube. The ventilator mode and rate will be set as per center practice, to ensure best standard of patient care.

Upon arrival to the ICU, the patient will be hemodynamically stabilized and placed on $FiO_2 = 1.0$ and $PEEP = 5$ cmH₂O (or greater, if clinically necessary, to achieve $SpO_2 > 92\%$ and $PaO_2 \geq 75$ mmHg).

The following will be assessed as per center practice (unless otherwise specified) on arrival to the ICU and recorded in the CRF, apart from SVR and PVR which will be calculated during data-management:

- PaO_2/FiO_2 ratio ($FiO_2 = 1$; $PEEP = 5$).
- Chest X-rays (see Appendix 1 for methodological details).
- BP, HR.
- CO, PA pressure, SVR, PVR, PCWP, CVP.

7.5.2. Assessment in the ICU

The following will be assessed during ICU stay and recorded in the CRF, apart from SVR and PVR which will be calculated during data-management. Measurement will be performed as per center practice, unless otherwise specified. For the purpose of this study, clinically diagnosed PGD is defined as:

- An episode of decreased $\text{PaO}_2/\text{FiO}_2$ ratio and chest X-ray results consistent with a PGD score of grade 3, which is not the result of some other secondary cause of graft dysfunction [Christie, 2005]. When diagnosed, the condition is considered clinically recovered for a PGD score of ≤ 1 .
- $\text{PaO}_2/\text{FiO}_2$ ratio. $\text{PaO}_2/\text{FiO}_2$ ratio will be measured at $\text{FiO}_2 = 1$ q24 hours, up to extubation or up to 72 hours after ICU admission, whichever occurs earlier. Patients on $\text{FiO}_2 < 1$ will be turned back to $\text{FiO}_2 = 1$ for 5 minutes before gas measurement. Additional $\text{PaO}_2/\text{FiO}_2$ ratio values obtained as per center standard of care in patients with clinical diagnosis of PGD will be recorded in the CRF up to the clinical recovery of the condition.
- Chest X-rays. A chest X-rays will be obtained 24 hours, 48 hours, and 72 hours after ICU admission (see Appendix 1 for details).
- BP, HR. Vital signs will be measured q12 hours up to ICU discharge or up to 5 days after ICU admission, whichever occurs earlier.
- CO, PA pressure, SVR, PVR, PCWP, CVP. Cardiopulmonary physiologic measurements will be assessed q12 hours when a PA catheter is present, up to ICU discharge or up to 5 days after ICU admission, whichever occurs earlier. Additional measurements obtained as per standard of care in patients with clinical diagnosis of PGD will be recorded in the CRF up to the clinical recovery of the condition.

For all measurements above, the actual date and time of assessment will be recorded in the CRF.

- A BAL will be performed during mechanical ventilation, in the interval between 12 and 24 hours after reperfusion, unless the patient is suffering from any clinical conditions which would be worsened by BAL procedures, in the opinion of the Investigator (see Appendix 1 for methodological details). Date and time of sampling will be recorded in the CRF along with location of BAL (lung, site) number of aliquots injected, amount recovered and summary of the most recent chest X-rays report. Specific reasons (hemodynamic instability, severe hypoxemia, etc.) for the decision to omit the BAL should be recorded in the CRF.

Renal (CLcr, urine output) and hepatic (bilirubin, transaminases) function will be tested at 12, 24, and 36 hours after the beginning of Investigation Product infusion.

Other clinical findings, including bronchoscopic and/or BAL findings, reports for all routine chest X-rays and thoracic CT scans, and results of routine biopsy will be copied into the CRF from the medical charts. AEs will be also recorded.

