4.2.1.2. Secondary efficacy (exploratory) endpoints

- Time profile of PaO₂/FiO₂ ratio measured at FiO₂ = 1 during mechanical ventilation at four potential time points: ICU admission (time 0) and then q24 hours, up to extubation or up to 72 hours after ICU admission, whichever occurs earlier. Additional data obtained as per center standard of care will be collected in patients with clinical diagnosis of PGD up to the clinical recovery of the condition.
- PGD score (stratified by single or bilateral transplant), evaluated according to the scoring system described by Christie et al. of the working group on primary lung graft dysfunction in the Scientific Council on Pulmonary Transplantation, International Society for Heart and Lung transplantation (2005; see Appendix 1 for methodological details). Specific planned comparison of PGD scores will be made at four time points: ICU admission (time 0), 24 hours, 48 hours, and 72 hours after ICU admission. In patients with clinical diagnosis of PGD additional scoring will be calculated up to the clinical recovery of the condition from available data as per center standard of care.
- Time to freedom from mechanical ventilation, defined as time between admission to the ICU and the initial time of first extubation (breathing off mechanical ventilation without a tube) which is maintained for more than 24 hours.
- Duration of ICU stay.
- ICU mortality, defined as vital status at the ICU discharge.
- Mortality, defined as any death occurring in the first 30 days post-transplant, regardless of hospital discharge.

- FEV₁ and FVC (stratified by single or bilateral transplant) measured at month 1, 6, and 12 post-transplant.
- BOS score (stratified by single or bilateral transplant) evaluated according to Estenne et al. (2002). BOS score will be measured at month 6, and 12 post-transplant.
- Cumulative acute rejection episodes, biopsy proven, evaluated according to Yousem et al. (1996) at month 6 and 12 post-transplant.
- Patient survival rate evaluated at month 6 and 12 post-transplant.
- Any additional information from BAL/biopsies performed according to standard of care in patients with clinical diagnosis of PGD will be collected up to the clinical recovery of the condition.

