9. STATISTICAL ISSUES

9.1. SAMPLE SIZE

The sample size has been estimated based on PaO₂/FiO₂ ratios immediately and at 24 hours from the results of 700 lung transplant operations at the Washington University. The database reports means and standard deviations for this endpoint of 329±137 mmHg at the initial ICU assessment and 315±117 mmHg at 24 hours.

A sample size of 50 in each group will have a 81% power to detect a difference in means of 70 mmHg (the difference between a placebo mean of 315 and a treated mean of 385, a 22% improvement) assuming that the common standard deviation is 137 using a two group t-test with a 0.05 one-sided significance level. Alternatively, a sample size of 50 in each group will have a 56% power to detect a difference in means of 50 mmHg (the difference between a placebo mean of 315 and a treated mean of 365, a 15% improvement) assuming that the common standard deviation is 137 using a two group t-test with a 0.05 one-sided significance level.

There is no currently available data to provide a knowledgeable estimate of the effect size in this study. If the effect size is smaller than 15%, the power of this study will be reduced and the chance of a Type II error is increased. Under such circumstances, this study would still provide valuable data regarding the effect size in the primary outcome variable as well as the results in all of the secondary, exploratory endpoints and subgroup analysis.

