14. APPENDICES

14.1. APPENDIX 1 - METHODOLOGICAL DETAILS

14.1.1. PGD score - ISHLT system for grading of severity of primary graft dysfunction [*Christie et al, 2004*]

Grade 0	$\text{PaO}_2/\text{FiO}_2 \geq 300$ mmHg; no radiographic infiltrates
Grade 1	$\text{PaO}_2/\text{FiO}_2 \geq 300$ mmHg + radiographic infiltrates consistent with pulmonary oedema
Grade 2	$200 \text{ mmHg} \leq \text{PaO}_2/\text{FiO}_2 < 300$ mmHg + radiographic infiltrates consistent with pulmonary oedema
Grade 3	$\text{PaO}_2/\text{FiO}_2 < 200$ mmHg + radiographic infiltrates consistent with pulmonary oedema

Any patient with no infiltrate on chest X-rays is automatically grade 0, regardless of $\text{PaO}_2/\text{FiO}_2$ value. If the patient is on nasal cannula for oxygen or $\text{FiO}_2 < 0.3$, the patient is graded as 0 or 1, based on chest X-rays. Any patient on extra corporeal membrane oxygenation is automatically grade 3. Any subject mechanically ventilated with FiO_2 greater than 0.5 or requiring nitric oxide beyond 48 hours from the time of transplant should be considered grade 3.

If multiple blood gas values are available, the worst $\text{PaO}_2/\text{FiO}_2$ ratio will be used for the purpose of this grading scheme.

PGD score will be evaluated at the following time points:

- Time-0 (T0): defined as within 6 hours of final lung reperfusion. The first blood gas in ICU is ideal for this. Ideally, measurement should be done on $\text{FiO}_2 1.0$ and PEEP =5 while still on mechanical ventilation.
- T24, T48, T72: Later times being measured at potentially multiple time points after 24 hours, up to 72 hours. Time will be measured following $T0 \pm 6$ hours.

Chest X-rays will be graded by an Investigator, and then validated by a (blinded) transplant radiologist.

In patients with clinical diagnosis of PGD additional time points will be considered up to the clinical recovery of the condition as per available data according to center standard of care.

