### 9.5.2.2 PGD score

Analysis of PGD score will be performed separately at time 0 and at 24, 48 and 72 hours after ICU admission. Two analyses, using Cochran-Mantel-Haenszel statistics from PROC FREQ within SAS, will be performed at each time point. The first will use type of transplant (single or double) as a stratification factor and will use the following SAS code:

```
Proc freq data=data1 (where=(time=x)) noprint ;  
  table tran_typ*PGD*treat/cmh out=ct_typ ;  
  output out=cmh type cmh ;  
run ;
```

As the randomization did not include type of transplant it is possible that there will be insufficient data within each of the cells to perform the analysis. This will be assessed after the Month 1 database lock.

The second analysis will use center as a stratification factor.

Both analyses will be performed for both the ITT and PP populations. For each analysis, the number and percentage of patients within each table cell will be presented, together with the second of the three p-values provided by PROC FREQ (labeled as Row Mean Scores Differ), and the corresponding Mantel-Haenszel odds ratio and the associated 95% confidence interval.

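### An extubated patient with infiltrates on FiO2 of 0.3 or more and no recorded gas has no PGD grade, and the SAP grading table widens that gap, so missing grades depend on the grade itself

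*Protocol*

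**What the plan says.** **Blood gases.** Protocol 7.5.2 schedules the ratio "q24 hours, up to extubation or up to 72 hours after ICU admission, whichever occurs earlier", and SAP 3.1 has the same stop. Gases taken as routine care are recorded only in patients with clinically diagnosed PGD, until recovery. Section 7.5.2 ties that diagnosis to a grade 3 picture.

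**Films and scores.** Protocol 7.5.2 schedules chest X-rays at 24, 48 and 72 hours with no stop at extubation. For the score, Protocol 4.2.1.2 (times counted from arrival in the ICU) says: "Specific planned comparison of PGD scores will be made at four time points: ICU admission (time 0), 24 hours, 48 hours, and 72 hours after". SAP 9.5.2.2 agrees: "Analysis of PGD score will be performed separately at time 0 and at 24, 48 and 72 hours after ICU admission".

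**Grading rules.** In Protocol Appendix 1 (14.1.1) a clear film is grade 0 whatever the ratio. With infiltrates, the ratio separates grades 1, 2 and 3. There are overrides for extracorporeal oxygenation, for ventilation above FiO2 0.5 and for nitric oxide beyond 48 hours. One shortcut needs no gas: "If the patient is on nasal cannula for oxygen or" an FiO2 below 0.3, the film alone decides between grade 0 and grade 1.

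**SAP version.** The PGD table in SAP 5 keeps the clear-film rule and the three ratio bands. It omits the cannula/low-FiO2 shortcut and all the overrides. SAP 1.2 declares no changes from the protocol.

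**Missing data.** Last-observation and zero-for-death substitution (Protocol 9.4.2, SAP 9.5.1) apply to the 0 and 24 hour ratio only. No rule is given for a missing PGD score. SAP 9.1 takes percentages over non-missing responses.

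**The concern.** A grade of 0 can always be assigned from the film, so it is never missing for want of a gas. A patient with infiltrates can be ungradable, and whether that happens depends on having been extubated. Missingness is thus tied to the value being measured and to an event after randomization that treatment may change; time to freedom from mechanical ventilation is itself an endpoint. At 24, 48 and 72 hours the Cochran-Mantel-Haenszel test would compare subsets of the two arms selected in this way.

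The stated objective is reduced severity of PGD, and the score is one of the few secondary endpoints to be tested formally. A distortion here would affect how the trial is read, even though the endpoint is labelled exploratory.

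**Working it through.** **1. The plan's own figures.** The only power figures concern the PaO2/FiO2 ratio. Protocol 9.1 states: "A sample size of 50 in each group will have a 81% power to detect a difference in means of 70 mmHg", and "56% power to detect a difference in means of 50 mmHg", "assuming that the common standard deviation is 137" and "using a two group t-test with a 0.05 one-sided significance level". The noncentral t distribution with 98 degrees of freedom gives 81.4% and 56.6%, so the figures reproduce. They do not concern the PGD score and are unaffected by this point.

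**2. Grading an extubated patient with no recorded gas** (Appendix 1 overrides aside):

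| Film and oxygen | Protocol Appendix 1 | SAP 5 table |
|---|---|---|
| Clear film | 0 | 0 |
| Infiltrates, nasal cannula or FiO2 < 0.3 | 1 | no grade |
| Infiltrates, FiO2 of 0.3 or more | no grade | no grade |

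**3. How many patients.** The documents give no extubation, infiltrate or oxygen-delivery rates. Assumptions: 50–70% extubated by 72 hours, infiltrates in 30–50% of those, FiO2 of 0.3 or more in 30–60% of those, and no usable gas in any of them.

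- Appendix 1: 0.5 × 0.3 × 0.3 = 4.5% to 0.7 × 0.5 × 0.6 = 21%, or 2.25 to 10.5 of 50 per arm.
- SAP table read literally: 0.5 × 0.3 = 15% to 0.7 × 0.5 = 35%, or 7.5 to 17.5 of 50 per arm.

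**4. Direction, by proportions.** Suppose 10 of 50 in an arm are truly grade 2–3 (20%) and 10 patients are ungraded.

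- None of the 10 is grade 2–3: 10/40 = 25%.
- Two are: 8/40 = 20%.
- Four are: 6/40 = 15%.

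The shift changes sign with the grades lost.

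**5. Direction, by mean grade.** Assume the same true mix in both arms: 40/25/20/15% for grades 0–3, mean 1.10. Assume extubation by grade of 60/60/40/10% on placebo and 80/80/60/20% on repertaxin. Let u be the share of extubated patients with infiltrates who cannot be graded. Grade 0 is kept in full; grade g ≥ 1 is kept in proportion p(g) × [1 − e(g) × u].

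Worked for u = 0.5:

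- Placebo: kept 0.400 + 0.175 + 0.160 + 0.1425 = 0.8775; mean (0.175 + 0.320 + 0.4275)/0.8775 = 1.051.
- Repertaxin: kept 0.400 + 0.150 + 0.140 + 0.135 = 0.825; mean (0.150 + 0.280 + 0.405)/0.825 = 1.012.
- Difference: −0.039, with no true effect.

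| u | Missing, placebo | Missing, repertaxin | Spurious mean difference | False favourable result |
|---|---|---|---|---|
| 0 | 0% | 0% | 0 | 2.4% |
| 0.10 | 2.5% | 3.5% | −0.006 | not simulated |
| 0.25 | 6.1% | 8.7% | −0.017 | 3.2% |
| 0.50 | 12.3% | 17.5% | −0.039 | 3.7% |
| 1.00 | 24.5% | 35.0% | −0.110 | 5.8% |

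The last column comes from 10,000 simulated trials per row with 50 per arm. It uses a two-sided 5% comparison of mean grade without strata, as a stand-in for the planned test. The row u = 1 is close to the SAP table read literally. Under these assumptions the bias favours the arm extubated sooner and is small unless most such patients are ungradable.

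**The case against.** **Appendix 1 can be read generously.** It does not confine grading gases to ventilated patients. It takes the worst ratio when several are available, and it treats FiO2 of 1.0 on the ventilator as ideal rather than required. The flow chart lists the ratio at 72 hours with no extubation footnote. This stands as far as it goes: a chart gas could be used. But for a patient without a prior grade 3 episode, 7.5.2 does not have that gas recorded, so the analysis would not contain it.

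**The most severe patients are partly covered.** After clinically diagnosed PGD, routine gases are recorded until recovery, if any are taken. This narrows the gap, but a patient whose true grade has never exceeded 2 does not enter that exception.

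**Not every ungraded patient fits the mechanism.** Protocol 7.5.2 lists the films under assessments during the ICU stay, so a patient who has left the unit may lack a film whatever it would have shown. That is a separate loss and does not remove this one.

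**Stronger readings the documents do not support.** A reader might infer that anyone on mask oxygen with infiltrates is ungradable. Under Appendix 1 that is so only at FiO2 of 0.3 or more. A reader might also infer that the arm extubated sooner must look worse, since ungraded patients leave the denominator. That holds only if few ungraded patients are grade 2–3: step 4 shows the shift vanishing or reversing, and step 5 gives the opposite direction.

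**The endpoint is exploratory and the size unproven.** Both are true. They limit the weight of the point without settling which grade these patients receive.

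**Conclusion.** The gap is real in both documents. Appendix 1 gives no grade to an extubated patient with infiltrates on FiO2 of 0.3 or more without a recorded gas. The SAP table, despite its statement of no changes, extends this to every extubated patient with infiltrates and no gas. Nothing in the missing-data rules closes it, so missing PGD grades depend on the grade and on extubation.

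The comparison at 24, 48 and 72 hours can therefore be biased. Size and direction depend on how many patients fall in the gap and which grades are lost, and the documents give neither. The ranges of 4.5–21% and 15–35% ungraded, and the rise in false favourable results from 2.4% to at most 5.8%, rest wholly on the assumptions shown. The point should be fixed, but it concerns a secondary, exploratory endpoint and does not touch the primary analysis.

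**What to change.** 1. Carry all the Appendix 1 grading rules into SAP 5: the nasal cannula/FiO2 below 0.3 rule and the extracorporeal oxygenation, ventilation and nitric oxide rules.
2. Extend the routine-care gas recording in Protocol 7.5.2 to all extubated patients within the 24, 48 and 72 hour windows, and grade from that gas with the delivered FiO2. Name the window: Appendix 6 allows ±2, ±4 and ±4 hours for the ratio but ±4, ±8 and ±8 hours for the film, and Appendix 1 refers to ±6 hours.
3. Where infiltrates are present, no gas exists and the cannula/low-FiO2 rule does not apply, leave the grade missing in the main analysis. Add sensitivity analyses assigning the best possible grade (1) and the worst (3). Grading these patients on the film alone would be simpler, but it would cap possible grade 2–3 patients at grade 1.
4. Tabulate, by arm and time point, how many patients were graded on film alone and how many were not graded.

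The cost is some chart transcription, two added analyses and one table; no new procedure is needed. Gases taken off the ventilator at an estimated FiO2 are less standardised than those at FiO2 of 1, which the report should state. SAP 1.1 puts randomization at about 60 patients, with the plan to be finalized before database lock, so the rules can still be set blind. Gases for patients already past 72 hours would have to be taken from their charts.
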